5.2 Subject enrolment and initiation of investigational product

The Principal Investigator will:

- 1. Obtain signed informed consent from the potential subject before any study specific procedures are performed
- 2. Assign the potential subject a unique enrolment number, beginning with "E0001001"
- 3. Determine subject eligibility. See Sections 4.1 and 4.2
- 4. Assign eligible subjects a unique subject number, beginning with "101"

If a subject withdraws from participation in the study, then his enrolment number cannot be reused.

Any subject who discontinues from the study before completion may be replaced at the discretion of the Investigator in order to ensure that data from a minimum of 4 evaluable subjects is obtained.

5.3 **Procedures for handling subjects incorrectly enrolled or initiated on investigational product**

Subjects who fail to meet the inclusion criteria or meet any of the exclusion criteria should not, under any circumstances, be enrolled or dosed. There can be no exceptions to this rule.

Where subjects that do not meet the selection criteria are incorrectly started on treatment, or where subjects subsequently fail to meet the study criteria post initiation, a discussion should

occur between the AstraZeneca Clinical Pharmacology Alliance Physician and the Investigator regarding whether to continue or discontinue the subject from treatment.

The AstraZeneca Clinical Pharmacology Alliance Physician is to ensure all such decisions are appropriately documented. In situations where an agreement cannot be reached, the subject should have their study therapy stopped.

5.4 Blinding and procedures for unblinding the study (Not applicable)

5.5 Treatments

5.5.1 **Identity of investigational product(s)**

The investigational product will be administered as a 2 mg/mL oral solution to achieve a 160 mg dose in an acceptable volume (80 mL). To obtain a solution of 2 mg/mL it is necessary to include citric acid monohydrate and tri-sodium citrate as buffers to control the pH to 4.5.

The 2 mg/mL radiolabeled solution contains diluted $[^{14}C]$ AZD8931 diffumerate, citric acid monohydrate, tri-sodium citrate, and water. [¹⁴C] AZD8931 difumerate (diluted with unlabelled AZD8931 difumerate to approximately 0.84 µCi/mg) is dissolved in 0.01 M citrate buffer to produce a clear, colourless oral solution. The investigational product will be provided as unit doses in Type III amber glass bottles.

Investigational product	Dosage form and stren	Manufacturer	
[¹⁴ C] AZD8931	Oral solution 160 mg AZD8931, 200	AstraZeneca	
Components	Quantity (% w/v)	Function	Standard
Diluted [¹⁴ C] AZD8931 difumerate ^a	0.2978	Active	AstraZeneca
Citric acid monohydrate	0.063	Buffer	Ph Eur, BP
Tri-sodium citrate dihydrate	0.157	Buffer	Ph Eur, BP
Water for injection	То 100	Solvent	Ph Eur

1 g of AZD8931 is equivalent to 1.489 g of AZD8931 difumerate.

5.5.2 **Doses and treatment regimens**

Each subject will receive a single oral dose of 160 mg $[^{14}C]$ AZD8931 administered on Day 1 as an oral solution. The dosing vessel will be rinsed with 2 x 50 mL water which must also be taken by the subject. This will give an effective dose equivalent of 4.7 mSv.

Water is allowed up to 1 hour predose and from 1 hour after dosing (except for water used to rinse the dosing vessel).

5.5.3 Labelling

Labels will be prepared in accordance with Good Manufacturing Practice and local regulatory guidelines. The labels will fulfil Good Manufacturing Practice Annex 13 requirements for labelling.

The labels will include blank lines for the E code and the Investigator's name. AstraZeneca will label each bottle with a permanently affixed label stating that the material is for Clinical Trial Use Only.

5.5.4 Storage

All investigational products should be kept in a secure place under appropriate storage conditions. The investigational product label will specify the appropriate storage conditions.

The investigational product will be supplied frozen (-20°C) and protected from light. Each 100 mL Type III amber glass bottle will have an 80 mL fill volume.

The investigational product will be thawed out and shaken according to the detailed handling instruction before dosing to subjects.

5.6 **Concomitant and post-study treatment(s)**

Use of concomitant medications, herbal supplements, and/or ingestion of foods that significantly modulate CYP3A4 and/or CYP2C6 activity or which are significantly metabolised by CYP3A4 and/or CYP2D6 should be avoided. Any prescribed or non-prescribed medication including drugs with hepatic enzyme-altering properties, such as St John's wort, antacids, analgesics, herbal remedies, vitamins, and minerals should be avoided during 2 weeks (or longer depending on the medication's half-life) before dosing until after Follow-up.

Subjects should abstain from using any medication, over-the-counter remedies, herbal medications, high-dose or "mega" vitamins, or medicines purchased via the Internet from 2 weeks before dosing until after Follow-up. Use of 1 g paracetamol 6 hourly (to a maximum daily dose of 4 g) is permitted, however the Investigator should be informed so it can be recorded.

Subjects should not use any eye drops or ointment for treatment of eye symptoms, unless prescribed by the Investigator, until 1 week after dosing.

Other medication, which is considered necessary for the subject's safety and well being, may be given at the discretion of the Investigator and recorded in the appropriate sections of the electronic Case Report Form (CRF).

5.7 Treatment compliance

The administration of the investigational product should be recorded in the appropriate sections of the CRF.

Treatment compliance will be assured by supervised dosing of the investigational product by the Investigator or delegate.

5.7.1 Accountability

The investigational product provided for this study will be used only as directed in the Clinical Study Protocol.

The study centre staff will account for the investigational product dispensed to the subject.

Study centre staff will account for all investigational products received at the study centre, unused investigational products and for appropriate destruction/return. Certificates of delivery, destruction/return should be signed.

5.8 Withdrawal from study

Subjects may be discontinued from the investigational product in the following situations:

- Subject decision. The subject is at any time free to discontinue treatment, without prejudice to further treatment
- AE
- Severe non-compliance to the Clinical Study Protocol as judged by the Investigator and/or AstraZeneca
- Risk to the subject as judged by the Investigator and/or AstraZeneca
- Incorrectly enrolled subject
- Subject is lost to Follow-up

5.8.1 **Procedures for withdrawal of a subject from the study**

Subjects are at any time free to withdraw from the study (investigational product and assessments), without prejudice to further treatment (withdrawal of consent). Such subjects will always be asked about the reason(s) and the presence of any AEs. If possible, they will be seen and assessed by an Investigator. Adverse events will be followed up (see Sections 6.3.3 and 6.3.4).

Any subject who discontinues from the study before completion may be replaced at the discretion of the Investigator in order to ensure that data from a minimum of 4 evaluable subjects is obtained.

6. COLLECTION OF STUDY VARIABLES

The timing of the assessments described in this section is detailed in Table 1 and Figure 1.

6.1 Recording of data

The Investigator will ensure that data are recorded on the electronic CRF as specified in the Clinical Study Protocol and in accordance with the instructions provided.

The Investigator will ensure the accuracy, completeness, and timeliness of the data recorded and of the provision of answers to data queries according to the Clinical Study Agreement. The Investigator will sign the completed electronic CRFs. A copy of the completed electronic CRFs will be archived at the study centre.

6.2 Data collection and enrolment

Each subject will undergo screening in the 28 days before Visit 2. This will consist of:

- 1. Obtaining written informed consent before starting any study specific procedures
- 2. Recording of demographic data (date of birth, sex, race)
- 3. Height, weight, and calculation of BMI
- 4. A standard medical, medication, and surgical history with review of the inclusion and exclusion criteria with the subject
- 5. A complete physical examination
- 6. Habits of nicotine and alcohol use
- 7. Vital signs
- 8. Recording of a resting 12-lead paper ECG
- 9. A blood sample for routine clinical chemistry and haematology, and screen for hepatitis B surface antigen, antibodies to hepatitis C virus and antibodies for HIV
- 10. A urine sample for routine urinalysis and drugs of abuse screen (excluding alcohol)
- 11. Assessment of AEs
- 12. Assessment of any concomitant medication
- 13. Ophthalmology assessment
- 14. Blood sample for pharmacogenetics (optional)

6.2.1 Follow-up procedures

A medical examination will be performed 5 to 10 days after the last sample collection. This will be similar to the one performed at the pre-entry visit and will include a complete physical examination, vital signs, recording of a 12-lead ECG, a blood sample for laboratory safety assessments, a urine sample for urinalysis, ophthalmology assessment, and assessment of any AEs or required medication.

6.3 Safety

The Principal Investigator is responsible for ensuring that all staff involved in the study is familiar with the content of this section.

6.3.1 Definition of adverse events

An AE is the development of an undesirable medical condition or the deterioration of a pre-existing medical condition following or during exposure to a pharmaceutical product, whether or not considered causally related to the product. An undesirable medical condition can be symptoms (eg, nausea, chest pain), signs (eg, tachycardia, enlarged liver), or the abnormal results of an investigation (eg, laboratory findings, ECG). In clinical studies, an AE can include an undesirable medical condition occurring at any time, including run-in or washout periods, even if no study treatment has been administered.

The term AE is used to include both serious and non-serious AEs.

6.3.2 Definitions of serious adverse events

An SAE is an AE occurring during any study phase (ie, run-in, treatment, washout, Follow-up), that fulfils one or more of the following criteria:

- Results in death
- Is immediately life-threatening
- Requires in-patient hospitalisation or prolongation of existing hospitalisation
- Results in persistent or significant disability or incapacity
- Is a congenital abnormality or birth defect
- Is an important medical event that may jeopardise the subject or may require medical intervention to prevent one of the outcomes listed above

For further guidance on the definition of a SAE, see Appendix B to the Clinical Study Protocol.

6.3.3 Recording of adverse events

Time period for collection of adverse events

Adverse events will be collected from time of signature of informed consent (screening) throughout the treatment period and including Follow-up.

Serious adverse events will be recorded from the time of informed consent.

Follow-up of unresolved adverse events

Any AEs that are unresolved at the subject's last AE assessment in the study will be followed-up by the Investigator for as long as medically indicated, but without further recording in the CRF. AstraZeneca retains the right to request additional information for any subject with ongoing AE(s)/SAE(s) at the end of the study, if judged necessary.

Variables

The following variables will be collected for each AE:

- AE (verbatim)
- The date and time when the AE started and stopped
- Maximum intensity
- Whether the AE is serious or not
- Investigator causality rating against the investigational product (yes or no)
- Action taken with regard to investigational product
- AE caused subject's discontinuation from study (yes or no)
- Outcome

In addition, the following variables will be collected for SAEs:

- Date AE met criteria for SAE
- Date Investigator became aware of SAE
- AE is serious due to
- Date of hospitalisation
- Date of discharge
- Probable cause of death

Clinical Study Protocol Drug Substance AZD8931 Study Code D0102C00007 Edition Number 1.0 Date

- Date of death
- Autopsy performed
- Causality assessment in relation to study procedure(s)
- Causality assessment in relation to other medication
- Description of AE

The following intensity ratings will be used:

- Mild (awareness of sign or symptom, but easily tolerated)
- Moderate (discomfort sufficient to cause interference with normal activities)
- Severe (incapacitating, with inability to perform normal activities)

The CTC grades 1 through 5 correspond to the above intensity ratings as follows: grade 1=mild AE, grade 2=moderate AE, grade 3=severe AE, grade 4=life-threatening or disabling AE, grade 5=death related to AE.

It is important to distinguish between serious and severe AEs. Severity is a measure of intensity whereas seriousness is defined by the criteria in Section 6.3.2. An AE of severe intensity need not necessarily be considered serious. For example, nausea that persists for several hours may be considered severe nausea, but not an SAE. On the other hand, a stroke that results in only a limited degree of disability may be considered a mild stroke but would be an SAE.

Causality collection

The Investigator will assess causal relationship between the investigational product and each AE, and answer "yes" or "no" to the question "Do you consider that there is a reasonable possibility that the event may have been caused by the investigational product?"

For SAEs causal relationship will also be assessed for other medication and study procedures. Note that for SAEs that could be associated with any study procedure the causal relationship is implied as "yes".

A guide to the interpretation of the causality question is found in Appendix B to the Clinical Study Protocol.

Adverse events based on signs and symptoms

All AEs spontaneously reported by the subject or reported in response to the open question from the study staff: "Have you had any health problems since the previous visit/you were last asked?", or revealed by observation will be collected and recorded in the CRF. When collecting AEs the recording of diagnoses is preferred (when possible) to recording a list of

Clinical Study Protocol Drug Substance AZD8931 Study Code D0102C00007 Edition Number 1.0 Date

signs and symptoms. However, if a diagnosis is known and there are other signs or symptoms that are not generally part of the diagnosis, the diagnosis and each sign or symptom will be recorded separately.

Adverse events based on examinations and tests

The results from protocol-mandated laboratory tests and vital signs will be summarised in the Clinical Study Report. Deterioration as compared to baseline in protocol-mandated laboratory values, vital signs, and other safety variables should therefore only be reported as AEs if they fulfil any of the SAE criteria or are the reason for discontinuation of treatment with the investigational product.

If deterioration in a laboratory value/vital sign is associated with clinical signs and symptoms, the sign or symptom will be reported as an AE and the associated laboratory result/vital sign will be considered as additional information. Wherever possible the reporting Investigator uses the clinical, rather than the laboratory term (eg, anaemia versus low haemoglobin value). In the absence of clinical signs or symptoms, clinically relevant deteriorations in non-mandated parameters should be reported as AE(s).

Any new or aggravated clinically relevant abnormal medical finding at a physical examination as compared with the baseline assessment will be reported as an AE.

6.3.4 Reporting of serious adverse events

All SAEs have to be reported, whether or not considered causally related to the investigational product, or to the study procedure(s). All SAEs will be recorded in the CRF.

If any SAE occurs in the course of the study, then Investigators or other study centre staff inform appropriate AstraZeneca representatives within one day ie, immediately but **no later than the end of the next business day** of when he or she becomes aware of it.

The designated AstraZeneca representative works with the Investigator to ensure that all the necessary information is provided to the AstraZeneca Patient Safety data entry site within one calendar day of initial receipt for fatal and life threatening events and within five calendar days of initial receipt for all other SAEs.

For fatal or life-threatening AEs where important or relevant information is missing, active follow-up is undertaken immediately. Investigators or other study centre staff will inform AstraZeneca representatives of any follow-up information on a previously reported SAE within one calendar day ie, immediately but **no later than the end of the next business day** of when he or she becomes aware of it.

The Investigator or other study centre staff should send relevant CRF modules by fax to the designated AstraZeneca representative.

The reference document for definition of expectedness/listedness is the Investigator's Brochure for the AstraZeneca drug.

6.3.5 Laboratory safety assessment

Blood and urine samples for determination of clinical chemistry, haematology, and urinalysis will be taken at the times indicated in Table 1.

The laboratory variables that will be measured are listed in Table 2.

Clinical chemistry	Haematology	Urinalysis
Serum (S)-Albumin	Blood (B)-Haemoglobin	Urine (U)-Haemoglobin
S-Alanine aminotransferase	B-Haematocrit	U-Protein
S-Aspartate aminotransferase	B-Erythrocyte	U-Glucose
S-Alkaline phosphatase	B-Leukocyte	U-Creatinine
S-Bilirubin, total	B-Leukocyte differential count	
S-Calcium, total	(absolute)	
S-Cholesterol	B-Platelet count	
S-Creatinine	B-Red cell count	
S-C-reactive protein	B-Reticulocyte count	
S-Glucose, fasting	B-Mean corpuscular volume	
S-Potassium	B-Mean corpuscular haemoglobin	
S-Sodium	B-Mean corpuscular haemoglobin	
S-Gamma glutamyltransferase	concentration	
S-Urea		
S-Free thyroxine		
S-Thyroid stimulating hormone		

Table 2Laboratory safety variables

The samples for clinical chemistry, haematology, and urinalysis will be analysed using routine methods at

Blood will be tested for hepatitis B surface antigen, antibodies to hepatitis C virus, and antibodies to HIV at the screening visit.

Urine will be tested at the screening visit and Day -1 for the following drugs of abuse: alcohol (only Day -1), methadone, cannabis, cocaine, benzodiazepines, amphetamine, methamphetamines (including ecstasy), opiates, barbiturates, phencyclidine, and tricyclic antidepressants. The test will be performed at the study centre. If a subject tests positive for drugs of abuse a retest will be performed, and they may be excluded from entering the study, as judged by the Investigator.

If any laboratory values outside the

reference limits are suspected to be of clinical significance, as judged by the Principal Investigator and/or AstraZeneca, the sampling will be repeated. Subjects in whom the suspected clinical significance is confirmed at repeated sampling will either not be included or, if already included (started treatment), the deviating values will be monitored until normalisation or for as long as the Investigator considers necessary.

For blood volume see Section 7.1

6.3.6 **Physical examination**

Physical examinations will be performed at the times indicated in Table 1.

A complete physical examination will be performed and will include an assessment of the general appearance, respiratory, cardiovascular, abdomen, skin, head and neck (including ears, eyes, nose, and throat), lymph nodes, thyroid, abdomen, musculo-skeletal (including spine and extremities), and neurological systems.

6.3.7 ECG

The ECG assessments will be performed at times indicated in Table 1.

6.3.7.1 **Resting 12-lead ECG**

Electrocardiograms will be recorded in the supine position after the subject has rested in this position for at least 10 minutes. Only the overall evaluation will be captured in the CRF. Any abnormalities (including QTc values) should be reviewed by a cardiologist or an appropriately qualified person.

The original ECG printouts with variables must be signed and dated and stored in the subject's medical record as source data.

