6.3.8 Vital signs

Vital signs assessments will be performed at the times indicated in Table 1.

6.3.8.1 **Pulse and blood pressure**

Supine blood pressure and pulse rate will be measured using standard equipment with an appropriate cuff size after 10 minutes rest on a bed.

6.3.9 **Ophthalmology**

Baseline and postdose ophthalmology assessments will be performed at the time indicated in Table 1

The same ophthalmic expert will perform ophthalmic assessments on each occasion where possible. The ophthalmic assessment will be performed at baseline and again post-study.

The following assessments will be performed in the order stated:

- Visual acuity (best corrected) using both distance and near vision charts and Amsler grid text
- Schirmer's test without anaesthesia read after 5 minutes (this test should be done before instillation of stains or dilatory agents) pre-study examination only
- Slit lamp examination:
 - Evert lid and assess for presence of tarsal, fornicial, bulbar, and circumcorneal hyperaemia. Before staining, photograph any abnormalities to be captured
 - Apply 1 drop of 2% fluorescein followed by 1 drop of normal saline
 - Photograph any abnormalities
- Fundoscopy following pupil dilation and intraocular pressure measurement will be performed at pre-study examination only, but may be repeated at the ophthalmologist's discretion. Fundoscopy may be the last appropriate test.

During the study the subjects will be asked to report if they experience any eye symptoms such as dry eyes, grittiness, or irritation. In case of clinically relevant ophthalmological abnormalities, an additional full examination (as detailed above) will be performed.

Any corneal changes must be monitored frequently, with therapeutic intervention as appropriate until resolution. Any abnormalities elicited will be recorded as an AE.

6.4 **Pharmacokinetics**

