11. EVALUATION AND CALCULATION OF VARIABLES

11.1 Calculation or derivation of safety variable(s)

All AEs will be collected for each subject from the time when informed consent is obtained (Visit 1) until the follow-up visit. Adverse events that occur before dosing will be reported separately.

Change-from-baseline variables will be calculated for the safety variables listed below, as the post-treatment value minus the value at baseline. The baseline values will be as follows:

• Clinical laboratory tests: Day -1

- Vital signs (including supine and standing blood pressure): Day 1 predose
- ECG: Day 1 predose

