For ECG parameters, the QT correction factor will be based on the Fridericia's formula. Further categorical summaries of absolute QT and QTcF values (more than 450 ms, more than

480 ms, and more than 500 ms) and change from predose values in QT and QTcF values (more than 30 ms, and more than 60 ms) will also be produced.

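### The protocol plans QT/QTcF category and change-from-predose summaries, but its ECG capture rule puts only an overall evaluation in the CRF and names no route for the numeric values

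*Protocol*

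**What the plan says.** **ECG analysis.** Section 12.2.2 states: "For ECG parameters, the QT correction factor will be based on the Fridericia's formula". It continues with "Further categorical summaries of absolute QT and QTcF values", using cut-offs of 450, 480 and 500 ms, and adds that "change from predose values in QT and QTcF values (more than 30 ms, and more than 60 ms) will also be produced". Section 11.1 defines change from baseline as the post-treatment value minus the baseline value, and takes Day 1 predose as the ECG baseline.

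**ECG capture.** Section 6.3.7.1 states: "Only the overall evaluation will be captured in the CRF". It then says: "The original ECG printouts with variables must be signed and dated and stored in the subject's medical record as source data". Section 6.2 describes the screening ECG as a paper recording.

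**Data flow.** Section 10 takes the final data from the EDC system. It also allows data that are not directly captured to be managed outside the main database and merged later, and gives safety laboratory results and AE coding as examples.

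**Blood pressure.** Section 11.1 lists the baseline as "Vital signs (including supine and standing blood pressure): Day 1 predose". Section 6.3.8.1 says "Supine blood pressure and pulse rate will be measured using standard equipment", and note a to Table 1 likewise gives supine blood pressure and pulse only.

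**The concern.** A stated capture rule conflicts with a stated analysis. An overall evaluation cannot be Fridericia-corrected, subtracted from a baseline or sorted into millisecond categories. If the eCRF is built from Section 6.3.7.1 as written, whoever programs the Section 12.2.2 tables will find no ECG interval in the EDC extract.

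At stake is the tabulated QT evidence under the secondary safety objective. Section 1.1 reports an in vitro potential for QT prolongation and arrhythmia, so the protocol had a reason to plan these tables. Section 6.3.3 adds to the point. Deterioration in protocol-mandated safety variables is to be reported as an AE only if it meets an SAE criterion or causes discontinuation. An asymptomatic QTcF rise of more than 30 or 60 ms might then be neither an AE record nor a value in the database, although it would still be on the printout.

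The standing blood pressure entry in Section 11.1 is a smaller mismatch of the same type: a derived variable with no measurement behind it.

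**Working it through.** The protocol gives no figure to reproduce here. The check traces each planned variable back to its collection, then counts what is affected.

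**1. What the planned summaries need.** Fridericia's correction is QTcF = QT / RR^(1/3), with RR in seconds (RR = 60 / heart rate). Each ECG must therefore supply a numeric QT and a numeric RR or heart rate. The change categories need both at predose and at each later time. Pulse from the vital signs does not fill the gap: it supplies no QT and is not the RR of the same tracing.

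**2. What is collected.**

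| Variable | Planned in | Collected according to | In the CRF as specified? |
|---|---|---|---|
| QT, absolute and change | 11.1, 12.2.2 | 6.3.7.1: on the printout | No |
| RR or heart rate from the ECG | 12.2.2 (implied by Fridericia) | 6.3.7.1: on the printout, assuming it is among the printed variables | No |
| QTcF, absolute and change | 12.2.2 | derived from the two rows above | No |
| Overall ECG evaluation | 6.3.7.1 | 6.3.7.1 | Yes |
| Supine blood pressure, change | 11.1 | Table 1 note a, 6.3.8.1 | Not restricted; measured at every scheduled time |
| Standing blood pressure, change | 11.1 | nowhere | Not measured |

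**3. How many ECGs are affected.** Table 1 and its note h schedule ECGs at screening, predose, 24 hours, Day 11 and follow-up.

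- All scheduled ECGs: 5 × 6 subjects = 30.
- The 6 screening ECGs precede the Day 1 predose baseline and cannot enter a change from predose, so the relevant set is 4 × 6 = 24.
- Post-dose ECGs, each giving one change value per variable: 3 × 6 = 18.
- Planned categories: (3 absolute + 2 change) × 2 variables = 10. None of the 10 can be filled from the CRF content that Section 6.3.7.1 specifies.

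**4. Whether another route is stated.** Section 10 permits externally managed data in general terms but does not name ECG. Its mention of direct device capture concerns capture onto the electronic CRF, which is what the ECG-specific sentence rules out for intervals. No section describes transcription or transfer of ECG intervals.

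**5. Standing blood pressure.** No visit schedules it, so the number of measurements is 0 and neither its baseline nor its change can be derived. Supine change from Day 1 predose is fully supported.

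**The case against.** The best defence is that the numbers will exist. The printouts are signed, dated and kept as source for every scheduled ECG, including the predose one. The capture rule limits the CRF and does not forbid another path. Section 10 allows external data to be merged, offers its examples only as examples, says the datasets sent to the sponsor will hold all study data, and leaves collection detail to a Data Management Plan that is not at hand. This stands in part. A reader might infer that the QT tables can never be produced, or that they will be empty; the documents do not support that. They support a narrower statement: the tables cannot be built from the data the protocol says will be captured, and no route for the numeric values is named. A Data Management Plan or SAP might supply the route, but the sentence in Section 6.3.7.1 would still need reconciling with Section 12.2.2.

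A reader might also infer that the safety assessment would come down to a normal or abnormal reading, or that QT would have to be recovered by hand after database lock. Neither is supported. Safety also rests on AEs, physical and ophthalmology examinations, vital signs and laboratory tests. Section 6.3.7.1 sends ECG abnormalities, QTc values included, to a cardiologist or other qualified person, and Section 11.1.1 adds an expert review of ECG data. Nothing in the protocol says when or how missing intervals would be recovered.

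The risk context is also mixed. Section 1.1 follows the in vitro signal with a statement that in vivo cardiovascular studies showed no QT prolongation. Section 1.4 reports no QTc change of clinical concern after single doses of 2.5 to 200 mg, and no clinically relevant ECG or vital-sign change at 160 mg in 24 subjects. This lowers the urgency but does not remove the contradiction.

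**Conclusion.** The contradiction is real and sits within the protocol. Section 6.3.7.1 keeps QT and RR out of the CRF, while Sections 11.1 and 12.2.2 commit to summaries that need them. It covers 24 ECGs from predose onward, 18 change values for each of QT and QTcF, and all 10 planned categories. The counts assume 6 subjects who complete every scheduled ECG, with no replacements and no unscheduled recordings.

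Severity is should-fix. The objective is secondary, the analysis is descriptive in 6 subjects, the values are retained as source, and the primary absorption, metabolism, excretion and PK objective is untouched. The standing blood pressure reference is a wording error and adds no weight to the ECG point.

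**What to change.** Amend Section 6.3.7.1 so that, for each scheduled ECG, QT and RR (or heart rate) reach the database together with the overall evaluation, either by eCRF entry or by a defined electronic ECG transfer named in Section 10. State that QTcF is derived in the analysis database by Fridericia's formula. QT plus RR or heart rate is enough; PR and QRS are not needed for the QT/QTcF summaries in Section 12.2.2. The same fields would serve unscheduled ECGs, since Section 12.2.2 counts outliers at unscheduled evaluations. Dropping the QT/QTcF categories from Section 12.2.2 would also remove the contradiction, but it would give up summaries the protocol set out to provide.

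Separately, reconcile the blood pressure baseline in Section 11.1 with Table 1 note a and Section 6.3.8.1, which provide for supine measurement only.

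The cost is a few extra data fields for values expected on the printouts, or one transfer specification, plus one wording change. No extra procedure or visit is needed.
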